2.5.3 EFFICACY RESULTS AT INTERIM ANALYSIS

As a result of the mortality in Control Arm (CRRT alone) being approximately 10% lower than published levels of 45-50%, further analysis was undertaken. As a result of the analysis, it was discovered that amount of time the patient was maintained in the recommended ionized calcium range (0.25-0.40 mmol/L per SCD-003 protocol) presented a difference in efficacy outcomes. One reason for the deficiency in clinical trial execution to ensure the protocol's riCa target range of ≤ 0.40 mmol/L be maintained could be attributed to the national shortage of injectable calcium. If the patient did not experience circuit clotting, the PIs emphasis of achieving and continuously maintaining the patient in the recommended ionized calcium range was not consistently adhered to. In addition, the injectable calcium shortage resulted in 9 of the 21 open clinical sites unable to enroll subjects due to low hospital inventories of injectable calcium.

Of the 134 subjects enrolled in the SCD-003 protocol at the time of the interim analysis, 19 SCD subjects (CRRT+SCD) and 31 control subjects (CRRT alone) were maintained in the protocol's recommended range ($(\leq 0.40 \text{ mmol/L}) \geq 90\%$ of the therapy time).

Table 6 details all cause mortality at day 60 (primary endpoint) of the treated subjects which received the recommended ionized calcium (riCa) and **Table 7** details all cause mortality at day 60 of the treated subjects which did not receive the recommended ionized calcium (nriCa).

Table 6: 60 Day Mortality of Subjects – Recommended Ionized Calcium Range (riCa)

60 Day Mortality riCa	CRRT + SCD N= 19	CRRT Alone N= 27*	Overall N=46
Alive	84% (16/19)	59% (16/27)	70% (32/46)
Dead	16% (3/19)	41% (11/27)	30% (14/46)
Pearson chi2(1) = 3.2793 Pr = 0.070			

*Three subjects LTFU (004-007, 007-025, 011-004). One subject withdrew consent (013-002).

Table 7: 60 Day Mortality of Subjects – Non Recommended Ionized Calcium Range

60 Day Mortality nriCa	CRRT + SCD N= 50	CRRT Alone N= 32*	Overall N=82
Alive	52% (26/50)	69% (22/32)	59% (48/82)
Dead	48% (24/50)	31% (10/32)	42% (34/82)
Pearson chi2(1) = 2.2555 Pr = 0.133			

*Two subjects LTFU (002-003, 011-002). Two subjects enrolled to CRRT alone arm (012-002, 003-015) however not treated.

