A borderline statistically significant difference in 60-day all cause mortality (primary endpoint) was found in the cohort where the patient was maintained for $\geq 90\%$ of the treatment in the protocol's recommended ionized calcium (riCa) target range of ≤ 0.40 mmol/L over those that were maintained $\leq 90\%$ of the treatment duration.

The secondary endpoints of renal replacement therapy dependency at day 60, mortality at day 28, number of ventilator free days at day 28 and mortality of the sub population of severe septic patients at day 60 were analyzed. No statistical significance was shown except for the secondary endpoint of dialysis dependency. Dialysis dependency showed a statistically significant difference between the patients maintained for $\geq 90\%$ of the treatment in the protocol's riCa target range of ≤ 0.40 mmol/L over those at $\leq 90\%$ of the treatment duration. See **Table 8**.

Table 8: Dialysis Dependency at Day 60 – Recommended Ionized Calcium Range

Dialysis Dependency at Day 60 riCa	CRRT + SCD	CRRT Alone
N	0/16	4/16
p-value		0.033

When a composite endpoint of all cause mortality (primary endpoint) or renal replacement therapy dependency (a secondary endpoint) at day 60 is analyzed, a statistical significance is observed. See **Table 9**.

Table 9: 60 Day Combined End Point of All Cause Mortality or Dialysis Dependency – Recommended Ionized Calcium Range

60 Day Combined End Point of All Cause Mortality or Dialysis Dependency – riCa	CRRT + SCD N=19	CRRT Alone N=27
	15.8%	55.6%
N	3/19	15/27
p-value		0.007

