6.2 CRRT PARAMETERS

6.2.1 CITRATE ANTICOAGULATION

Each participating clinical site will use their regional citrate anticoagulation protocol. The clinical site is responsible to achieve, and maintain a serum post filter ionized calcium level of <0.40 mmol/L throughout the entire observation period (day and night). The serum post filter ionized calcium level will be collected from the CRRT Circuit post SCD [REDACTED]

To alleviate the metabolic derangements associated with regional citrate based anticoagulation:

- a) *Alkalosis:* Patients with an arterial pH <7.40 at enrollment will initiate CRRT with solutions containing either 25 or 35 meq/L

of base as directed by local standard of care. During the study, if the patient's arterial pH increases to >7.45 OR the patient's serum bicarbonate increases to >35 meq/L, the CRRT solution will be changed to a base concentration of 25 meq/L, OR 0.9% NaCl will be added dialysis fluid to correct the alkalosis per local standard of care.

b) *Citrate lock:* If the patient develops citrate lock, as defined by a serum ionCa <0.95 mmol/L and a total serum Ca >12.5 meq/L, the citrate infusion will be discontinued OR the CRRT clearance will be increased by 50% per local standard of care, AND CRRT circuit Ca and patient Ca will be checked at least every one hour. For centers that stop citrate, once the patient ionCa is >1.0 mmol/L, the citrate will be restarted at 50% of the previous rate, and hourly ionCa pairs will be rechecked x 3 to ensure a stable patient ionCa >1 mmol/L and stable circuit ionCa <0.40 mmol/L.

Of importance the clinical plan is to monitor the perfusion circuit iCa levels at least q1h at the initiation of regional citrate anticoagulation (RCA) until a steady state iCa range is between 0.25 to 0.40 mmol/L. Once established, iCa levels both in the circuit and in the patient will be monitored q6h. If the iCa is outside the targeted range or alterations in citrate or calcium infusion rates are made, iCa levels are measured at least q1h until targeted ranges are once again achieved. Of importance, for efficacy of SCD treatment, iCa levels must be maintained in the recommended range at least 90% of the time, based on a sensitivity analysis showing that the mortality endpoint difference was lower with target iCa 80-85% of total treatment in clinical trial SCD-003.

The protocol example identified in **Appendix K** may be utilized.

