6.4 STUDY OBSERVATION PERIOD

The Study Observation Period begins when the patient starts treatment and will continue up to a maximum of 168 hours from the time of Observation Start. **Patient will begin the Observation Period before the patient has reached 12 hours on CRRT.** A patient may begin CRRT therapy and SCD treatment at the same time, which would also mark the beginning of the Study Observation Period.

This observation period has been broken into seven 24 hour time periods. It ends when the patient has reached 168 hours in the observation period or when the patient meets the termination criteria outlined in **Section 7.2** as determined by the Principal Investigator or Medical Team at the participating Clinical Site.

All tests are scheduled on a 24 hour cycle, or once a day, and can be scheduled to be drawn around each participating site's ICU blood drawing schedule, with the exception of any test that requires a specific draw frequency.

The following information will be obtained for patients enrolled during the study observation period on a daily basis unless otherwise specified:

- **Vital Signs/Physical Assessment**
 - Temperature
 - Blood Pressure , heart rate
 - Urine Output (previous 24 hours)
 - Net Fluid Balance (previous 24 hours)
- **Clinical Laboratory Tests**
 - CBC with differential – every 12 hours (+/- 4 hours)
 - BUN, Creatinine
 - Na, K, Cl, HCO₃, Ca, ionized Ca, Mg, PO₄
 - ALT, AST, Bilirubin, ALP, Total Protein, Albumin, Glucose
 - PT, PTT, INR
- **Respiratory**
 - Status – Ventilator support (yes/no; date of extubation)
 - If on Vent: FiO₂
 - If on Vent with an arterial line: Arterial Blood Gas
 - If on Vent without an arterial line: Arterial Blood Gas (if available)
- **Blood for Research**
 - Collect at hours 48, 96, 144, and end of study (+/- 4 hours). If study observation period ends prior to hour 168, collect at end of study observation period. Blood for biomarkers will be collected as close as possible to the time of SCD scheduled changes in the days required (+/- 4 hours) if practical.
 - Blood sample will be sent to an outside laboratory for testing of biomarkers

- **CRRT Parameters (Start at hour 0)**
 - Parameters include modality, blood flow rate, net fluid removal, dialysate or replacement solution flow rate, citrate infusion rate, calcium replacement rate.
 - System performance (circuit survival - event driven)
 - Post filter ionized calcium (+/- 1 hour)

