Therapy Initiation	Q 1 hr. until post filter iCa level <0.40 mmol/L; then Q 6hr.
After any Calcium or Citrate rate change	Q 1 hr. until post filter iCa level <0.40 mmol/L; then Q 6hr.
After any Interruption: Recirculation, Procedure, Restart	Q 1 hr. until post filter iCa level <0.40 mmol/L; then Q 6hr.

- **SCD Performance (Start at hour 0)**
 - SCD [REDACTED] performance (event driven)
 - SCD and SCD Blood Tubing Set Change every 24 hour (+/-4 hour)
- **Other (Event Driven)**
 - Acknowledgement (yes/no) to critical medications administered to the patient
 - Adverse Events
 - Diagnostic/Therapeutic Procedures
 - Microbiology/culture data

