7.2. TREATMENT DISCONTINUATION CRITERIA

Patients may be withdrawn from therapy prior to hour 168 for a variety of reasons. When therapy is discontinued prior to hour 168, the follow-up period will immediately begin and data will continue to be collected per protocol.

The Principal Investigator will assign a primary reason for therapy termination utilizing the categories listed in 7.3 and 7.4 below, and if appropriate, one or more subcategories.

7.3. CLINICAL CRITERIA:

1. Improvement in Clinical Status

If a patient's condition improves (e.g. renal condition has improved to the extent that CRRT can be discontinued or hemodynamic status has improved so that the dialysis modality can be changed from CRRT to IHD) treatment may be discontinued before the 168 hour treatment period. The decision to discontinue treatment based upon improvement in clinical status will be made by the Principal Investigator.

2. CRRT related medical events

Such as persistent leukopenia, neutropenia or thrombocytopenia based upon PI's clinical assessment.

3. SCD related medical events

Such as persistent leukopenia, neutropenia or thrombocytopenia based upon PI's clinical assessment of relationship to SCD.

4. CRRT Failure/Malfunction

Failure of the CRRT device and/or circuit, including inability to maintain vascular access that requires treatment to be discontinued prior to hour 168 of therapy.

5. SCD Failure/Malfunction

Any failure of the SCD █ that requires treatment to be discontinued prior to hour 168 of therapy e.g. clotting or evidence of leakage in the SCD █ or inability to maintain a patent circuit.

6. Death**7. Withdrawal of life support****8. Concomitant Medical Conditions**

Need for medical, surgical or diagnostic procedures that necessitate discontinuation of SCD treatment for longer than the allowable 12 hours per 24 hour period.

9. Regional Citrate Anticoagulation Intolerance

All patients must be able to tolerate and achieve satisfactory regional citrate anticoagulation. Tolerance of regional citrate anticoagulation is defined as achieving:

- Two (2) consecutive circuit ionized calcium levels of < 0.40 mmol/L (or < 1.6 mg/dL),
- At least 30 minutes apart, and
- Within the first 12 hours of CRRT initiation.

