The Prospective Pediatric CRRT (ppCRRT) database will be used as a control for the CRRT treatment related factors including: patient age, gender, primary cause of AKI, total treatment duration, CRRT modality (CVVH, CVVHD, CVVHDF), CRRT small solute clearance (ml/1.73m²/hour), baseline estimated GFR (using the original Schwartz formula, which was used in the ppCRRT), urine output in the 24 hours prior to CRRT initiation (ml/kg/hour), percent fluid overload at CRRT initiation based on admission ICU weight, vasoactive medication number at time of CRRT initiation and mean airway pressure at CRRT initiation.

An additional analysis will also evaluate patients who have achieved targeted iCa levels during 90% of treatment time and those who do not.

In summary this protocol meets all criteria necessary for clinical scientific inquiry related to a test of hypothesis in a well monitored environment focused on patient safety during the conduct of the study. Basic statistics will be performed on the data sets along with historical data comparisons and subjected to subset analysis where appropriate. The results will help to guide the design of a future pivotal study of this device.

The rational for therapy, study objectives and endpoints, design, inclusion and exclusion criteria are explicitly defined. Patient safety parameters are well documented including safety reporting, safety observations and assays, procedures for patient withdrawal and study discontinuation criteria along with monitoring device integrity and performance. Lastly, a review of all prior SCD human study safety data is included in the protocol for full disclosure to study investigators and the informed consent document includes a full description of all known and potential risks of the device treatment.

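### Splitting patients on 90% of treatment time at target iCa is a post-baseline grouping tied to treatment length, and is open to bias of unknown direction and size

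*Combined protocol and SAP*

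**What the plan says.** Section 11 gives the analysis one sentence: "An additional analysis will also evaluate patients who have achieved targeted iCa levels during 90% of treatment time and those who do not". It names no outcome, no baseline adjustment, no rule for short courses and no method for assigning time between samples.

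The threshold comes from Section 6.2.1, which says that for efficacy "iCa levels must be maintained in the recommended range at least 90% of the time" and rests this on a sensitivity analysis of SCD-003.

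Three other sections determine the grouping:

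- **Length of treatment.** Under Section 6.4 observation "will continue up to a maximum of 168 hours from the time of Observation Start". Sections 7.2 and 7.3 let it end sooner, for death, withdrawal of life support, citrate intolerance or improvement. In the last case "treatment may be discontinued before the 168 hour treatment period".
- **Start-up.** Section 6.4 schedules circuit iCa "Q 1 hr. until post filter iCa level <0.40 mmol/L; then Q 6hr". Section 7.3 item 9 requires two consecutive values below 0.40 mmol/L "Within the first 12 hours of CRRT initiation"; otherwise SCD stops.
- **Minimum exposure.** Section 11 sets 72 h on SCD for inclusion in the final outcome analysis. It does not say whether that covers the iCa comparison.

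For SCD-003, Section 2.5.3 reports that "19 SCD subjects (CRRT+SCD) and 31 control subjects (CRRT alone)" were in range for at least 90% of therapy time. It presents the borderline mortality result as patients at or above 90% "over those that were maintained" in range for 90% or less.

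**The concern.** A patient's group is fixed only at the end of treatment, and the events that end treatment are themselves outcomes or close to them. Off-target time is expected mainly at start-up, so it is a large share of a short course and a small share of a long one. Anyone who fails the 12 h citrate tolerance rule must stop SCD, and so tends to be both short-course and a non-achiever. Off-target time can also follow from illness: for citrate lock, Section 6.2.1 allows the citrate infusion to be stopped.

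A difference between the groups would therefore mix any effect of iCa with treatment duration and severity. In a single-arm study no concurrent control can separate them. Section 11 says the results will help guide the design of a pivotal study, so a difference read as an iCa effect could carry over into that design.

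**Working it through.** **1. Reproduce the SCD-003 figures (Section 2.5.3).** Pearson chi-square without continuity correction:

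| Table | Deaths, SCD v CRRT alone | chi-square | p | stated p |
|---|---|---|---|---|
| 6, in range | 3/19 v 11/27 | 3.279 | 0.070 | 0.070 |
| 7, out of range | 24/50 v 10/32 | 2.256 | 0.133 | 0.133 |

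Both reproduce. They also show what was tested: SCD against CRRT alone within a stratum. The accompanying text describes a contrast between patients at or above 90% and those at or below it. Table 8 (dialysis dependency) has the same mismatch.

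**2. Is the SCD-003 split balanced by arm?** Achievement was 19/69 = 27.5% on SCD and 31/65 = 47.7% on CRRT alone, Fisher p=0.020. Comparisons within a stratum are therefore no longer protected by randomisation. Odds ratios for death, SCD v CRRT alone:

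- in range: (3×16)/(16×11) = 0.27
- out of range: (24×22)/(26×10) = 2.03
- interaction: log OR = ln 0.27 − ln 2.03 = −2.01, SE 0.88, p=0.023
- overall (Table 5): 27/69 = 39.1% v 21/59 = 35.6%, chi-square p=0.68

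The effect reverses between strata, with no overall difference.

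**3. How the criterion depends on duration.** Allowed off-target time = 0.10 × treatment hours. Shortest course that can reach 90% = 10 × off-target hours.

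| Treatment length | Allowed off-target time |
|---|---|
| 24 h | 2.4 h |
| 72 h | 7.2 h |
| 120 h | 12.0 h |
| 168 h | 16.8 h |

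As an illustration, 6 h off target is 75% in range at 24 h (18/24) and 96% at 168 h (162/168). A patient with 10 h off target cannot qualify before 100 h, and one with 12 h not before 120 h, even with perfect control afterwards.

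**4. Effect of the 72 h minimum.** If it applies, every included patient is allowed at least 0.10 × 72 = 7.2 h, so duration no longer matters for total off-target time up to 7.2 h. Above that it still does.

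**5. Size and direction if iCa has no effect.** This is a simulation of 24 scenarios with 600,000 patients each. The assumptions, none from the documents, are:

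- start-up off-target time uniform 2–12 h
- later off-target share uniform 0–10%, unrelated to outcome
- 60-day mortality 35% or 50%
- early stopping in 20–60% of those who die and 20–80% of survivors
- early stop times uniform 12–168 h

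Non-achiever minus achiever mortality ran from −19 to +13 percentage points; with the 72 h minimum, from −10.5 to +6.3. Achievers looked better only when early stopping was commoner among those who died. The difference was about zero when stopping was equally common, and reversed otherwise.

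**6. Direction in SCD-003.** Achievers v non-achievers within arm:

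- SCD: 3/19 = 15.8% v 24/50 = 48.0% dead, Fisher p=0.026
- CRRT alone: 11/27 = 40.7% v 10/32 = 31.3% dead, difference +9.5 points (95% CI −15.0 to +34.0), Fisher p=0.59

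**The case against.** The best defence is one of scale. This is one additional analysis in at most 30 patients, in a pilot that Section 11 says is not powered and not designed to assess efficacy. The 72 h minimum may already remove short courses. SCD can also start up to 12 h after CRRT, so some citrate titration may fall before SCD time begins. Those points limit the importance and perhaps the size of the problem. They do not remove it: small numbers do not protect against bias, and the plan says neither whether the 72 h rule applies nor when the clock for treatment time starts.

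A reader might infer that the split will favour achievers whatever iCa does. The documents do not support that. Section 7.3 ends treatment early for improvement as well as for death, so patients who do well can also become non-achievers. The CRRT-alone arm of SCD-003 leans against achievers, though inconclusively.

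A reader might also take the higher out-of-range mortality on SCD (48% v 31%) as an established safety signal. It comes from the same post-randomisation stratum and has p=0.133. Section 2.5.2 records that the DSMB had no safety concerns with the outcomes shown there.

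Nor should all 128 SCD-003 patients be pooled (14/46 v 34/82, p=0.22) as the precedent for this trial. Every patient here receives SCD, so the nearer analogue is SCD patients only, where achievers did better. That contrast is open to the same bias.

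**Conclusion.** The concern holds as a matter of design. The grouping is post-baseline, depends mechanically on treatment length and has no planned safeguard, so a difference between groups cannot be read as an effect of iCa. The arithmetic of the 90% criterion needs only the documents' own figures. The size and sign of the bias do not follow from them: the range of −19 to +13 points rests on assumed stopping patterns and shows only that either direction is possible. The SCD-003 evidence for the threshold is also a post-randomisation split, with unequal achievement by arm and no overall mortality difference, and the text misdescribes the contrast tested. This should be changed, but it affects an additional, unpowered analysis and not the trial's safety evaluation.

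**What to change.** 1. In Section 11, replace the whole-course split with a landmark analysis. Measure time-weighted iCa in range over a fixed early window, for example the first 24 h of SCD, as a continuous share or with a cut-off stated in advance. Include patients alive and on SCD at the end of the window, and count outcomes from then.
2. Show PRISM II by group, and adjust for it only if numbers allow.
3. State one iCa range for the classification. Sections 2.5.1, 2.5.3, 6.2.1 and 6.4 variously give 0.25–0.40, at most 0.40 and below 0.40 mmol/L, and must be reconciled. State also whether the 72 h minimum applies to this analysis.
4. Label the result descriptive and not evidence of an iCa effect.
5. In Sections 2.5.3 and 6.2.1, describe the SCD-003 split as post-randomisation. In 2.5.3, correct the text so that it matches the SCD v CRRT-alone comparison in Table 6.

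The cost is wording and a little programming. Patients off SCD before the landmark leave this one analysis. An early window reflects start-up control more than later control, and a 90% cut-off at 24 h would allow only 2.4 h off target. Confounding by severity would remain.

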12. DATA COLLECTION – STUDY MONITORING AND AUDIT

The Principal Investigator is responsible for assuring the accuracy and completeness of all study documentation. Monitoring will be conducted within ICH/GCP Guidelines and CytoPherx, Inc. Clinical Monitoring Plan to ensure the following:

- The facilities continue to be acceptable.
- The protocol is appropriately followed.
- Any agreed upon changes to the protocol have been approved by the IRB and approval has been received in writing by CytoPherx, Inc.
- Accurate, complete and current records are maintained and available for all patients.
- For each subject, collection of protocol-required data and entry of that data into the CRFs must be completed as soon as reasonably possible following that subject's last day in each study period.
- The information recorded and submitted to CytoPherx, Inc. is representative of the patient's record and other supporting documentation.
- Accurate, complete and timely adverse event reports for serious adverse events are submitted to CytoPherx, Inc.
- The Principal Investigator continues to assume primary responsibility for the study.

The Investigator or designee must, upon request, provide to the Clinical Research Associate (CRA), Quality Assurance Auditor, or FDA Investigator the necessary study records for a thorough review of the study's progress. These records include, but are not limited to, original documents and records, such as hospital and clinic charts, consent forms, and laboratory records. The Principal Investigator is required to notify the Sponsor immediately of the following:

- Withdrawal of IRB Approval
- Any protocol violations or protocol deviations related to study device use
- Notification that Informed Consent was not obtained or consent was withdrawn
- Any other instance in which the Investigator or Sponsor deems it necessary

